8.1. General Considerations

All statistical analyses will be conducted using SAS version 9.3 or later (SAS Institute Inc., Cary, NC) or R version 2.14 or later (R Development Core Team, 2012), and other validated statistical software as required. All output will be in Microsoft Word or RTF format, converted to PDF. Continuous variables will be summarized with means and standard deviations or as medians and interquartile ranges. Categorical variables will be summarized with the number and proportion of Subjects in each category. Binary outcomes will be presented as proportions with corresponding 95% confidence limits.

The primary efficacy endpoint and associated secondary efficacy endpoints are assessed at the Primary Endpoint Assessment Visit.

8.2. Study Populations

Several Cohorts are defined.

Intent to Treat (ITT) Cohort consists of all randomized Subjects who are not in the Surgical Roll-In group. This is the primary analysis population for the primary efficacy endpoint. The primary efficacy endpoint will be assessed in the ITT cohort. Additionally, the following analysis populations are defined. The primary efficacy endpoint will also be assessed in the per-protocol and completer cohorts. The secondary efficacy endpoints will also be assessed in the ITT cohort.

Surgical Roll In Cohort consists of all Subjects implanted in the Surgical Roll In group.

Per-protocol: Subjects within the ITT cohort receiving the correct randomized treatment, meeting the enrollment criteria, compliant with delivery of stimulation at least 80% of the maximum possible sessions delivered, and who have no other major protocol deviations affecting the primary endpoint evaluation will be considered to be part of the Per Protocol population.

Completers: All randomized Subjects who complete the Primary Endpoint Assessment Visit and associated endpoint assessments, regardless of compliance with the delivery of stimulation or the requirement to maintain constant medications.

Crossover Cohort: All Subjects in the Crossover Group who met the inclusion criterion 2 for low back pain (Low Back Pain VAS of ≥ 6.0 cm and ≤ 9.0 cm (on a 10cm scale)) and inclusion criterion 3 for ODI (Oswestry Disability Index score $\geq 21\%$ and $\leq 60\%$) at the time of crossover.

The primary efficacy endpoint and secondary efficacy endpoints will also be assessed in the Per-protocol and Completer cohorts.

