Treatment Arm	ReActiv8 implanted and configured to deliver stimulation at a Subject-appropriate level and Subjects instructed to deliver stimulation in two 30-minute sessions per day (the Treatment group).
Control Arm	ReActiv8 implanted and configured to deliver minimal stimulation, and Subjects instructed to deliver stimulation in two 30-minute sessions per day (the Control group).
Randomization	Subjects meeting all eligibility criteria who have been implanted with ReActiv8 will be randomized post-implant to either the Treatment group or the Control group. Randomization will be performed according to a random permuted block design stratified by clinical site with a 1:1 allocation ratio for Treatment vs. Control.
Anticipated Sample Size	Initial estimate: 128 randomized Subjects implanted with ReActiv8 in the intent to Treat cohort of the study, plus up to 80 Subjects implanted in the Surgical Roll In group. An adaptive statistical design using a single interim look will be used for sample size re-estimation when at least 50% of the implanted Subjects have completed the Primary Endpoint Assessment Visit. Up to 800 Subjects will be enrolled to account for screen failures prior to implant, Surgical Roll In, drop outs, and possible increase in numbers for the intent to treat analyses after the interim look.
Anticipated Number of Sites	There will be up to 40 Investigational sites performing implants. Each site will have a Site Principal Investigator who may or may not be the implanting physician. One or more Sub-investigators per site (or affiliated site if the affiliated site has a different Ethics Committee or IRB) may be used for example for device implantation and Subject recruitment.

Surgical Training and Surgical Roll In	All physicians who will implant any portion of the system will be trained as outlined in the Training Strategy. Following training, up to the first two Subjects implanted by the same physician may be prospectively included in a Surgical Roll In group. Subjects included in the Surgical Roll In group will be randomized to Treatment or Control with a single group randomization, and be analyzed as a separate cohort (the Surgical Roll In Cohort).

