4.4.2. Surgical Roll In Phase

Following training, up to the first two Subjects implanted by the same implanting physician may be prospectively included in a Surgical Roll In group and not included in the Intention To Treat Cohort. The Surgical Roll In phase for each implanting physician will be deemed complete upon consultation with the implanting physician and the Sponsor. In some cases, there will be no Surgical Roll In phase, for example if the implanting physician participated in the ReActiv8-A Trial. Note that Subjects included in the Surgical Roll In Phase who are not successfully implanted are not included in the Surgical Roll In group.

All Subjects implanted in the Surgical Roll In group will be randomized to either Treatment or Control, and follow the identical visit schedule as Subjects included after the Surgical Roll In phase. With approximately 40 implanting physicians and up to 2 Subjects in the Surgical Roll In phase per implanting physician, up to 80 Subjects may be included in the Surgical Roll In group.

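### The SAP's Completer population is not limited to the ITT Cohort, so read literally it admits Surgical Roll In Subjects to supporting efficacy analyses, contrary to the rule that they form a separate cohort

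*SAP*

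**What the plan says.** SAP 8.2 sets out the efficacy populations one after another:

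- ITT: "Intent to Treat (ITT) Cohort consists of all randomized Subjects who are not in the Surgical Roll-In group".
- Per-protocol opens: "Per-protocol: Subjects within the ITT cohort receiving the correct randomized treatment".
- Completers opens: "All randomized Subjects who complete the Primary Endpoint Assessment Visit and associated endpoint assessments". It then adds that adherence to stimulation and to constant medication does not matter. It has no ITT limit and no Roll In exclusion.

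SAP 8.2 assigns both the primary and the secondary efficacy endpoints to the Completer cohort as additional analyses. SAP 8.5.2 repeats this for the primary endpoint under supporting analyses.

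On the Roll In group, Protocol 4.4.2 states: "All Subjects implanted in the Surgical Roll In group will be randomized to either Treatment or Control, and follow the identical visit schedule" as later Subjects. The same section says that early Subjects of an implanting physician "may be prospectively included in a Surgical Roll In group and not included in the Intention To Treat Cohort". Protocol Table 1 (Section 2.4) says that they "will be randomized to Treatment or Control with a single group randomization, and be analyzed as a separate cohort (the Surgical Roll In Cohort").

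**The concern.** The three definitions stand in one section, and two of them deal with Roll In: ITT by an explicit exclusion, Per-protocol by sitting inside ITT. The third does neither. A programmer who builds the Completer flag from SAP 8.2 would include every randomized Subject who finished the endpoint visit, and Roll In Subjects meet that description.

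A Completer analysis exists to show whether the ITT conclusion depends on how missing endpoints are handled. That reading requires the two populations to differ only by the Subjects without an endpoint assessment. If Roll In Subjects are added as well, the populations differ in two ways at once, and a difference in results (or agreement between them) cannot be put down to missing data alone. The added Subjects are the first cases of their implanting physicians. They are also randomized under an arrangement that the synopsis describes differently from the site-stratified permuted blocks of the main trial.

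**Working it through.** **Does the literal definition reach Roll In Subjects?**

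1. Are they randomized? Yes (Protocol 4.4.2 and Table 1).
2. Do they have a Primary Endpoint Assessment Visit? Yes, their visit schedule is the same (Protocol 4.4.2).
3. Does the Completer definition exclude them or refer to ITT? No (SAP 8.2).
4. Does all-randomized by itself mean ITT in this SAP? No. SAP 7.2 and SAP 8.2 both describe ITT as randomized Subjects with Roll In taken out, so the unqualified phrase is the wider set.
5. Does another section supply a rule for pooling Roll In into efficacy? No. The Roll In poolability analysis belongs to safety (Protocol 4.7.4; SAP 8.8.1 and 8.8.2). SAP 7.4 tests whether the odds ratio for response is the same across sites, which is not a comparison of ITT with Roll In.

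**The plan's own counts**

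- Roll In ceiling, from about 40 physicians (Protocol 4.4.2: "up to 2 Subjects in the Surgical Roll In phase per implanting physician, up to 80 Subjects may be included in the Surgical Roll In"): 40 × 2 = 80.
- ITT (Protocol 4.7.1.2; SAP 6.1): 116 evaluable; 116 × 1.10 = 127.6, rounded up to 128 randomized.
- Total: 128 + 80 = 208, as in Protocol 4.4.

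**Roll In share of a literal Completer cohort**

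Share = R / (N + R), where R is the number of Roll In Subjects and N the ITT size. Counting everyone randomized gives the same share as counting completers when completion is equal in the two groups.

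| ITT size N | Roll In R | Share |
|---|---|---|
| 128 | 20 (assumed) | 20/148 = 13.5% |
| 128 | 40 (assumed) | 40/168 = 23.8% |
| 128 | 80 (ceiling) | 80/208 = 38.5% |
| 232 (2 × 116, cap in SAP 8.7) | 80 | 80/312 = 25.6% |
| 256 (2 × 128) | 80 | 80/336 = 23.8% |

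At the planned retention of 116/128, 80 Roll In Subjects become 80 × 116/128 = 72.5, about 72 completers. The share is then 72/(116 + 72) = 38.3%, essentially unchanged. Only unequal completion moves it: if all 80 Roll In Subjects finished but only 116 ITT Subjects did, it would be 80/196 = 40.8%.

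**After the fix:** R = 0. The largest possible Completer cohort at the initial size falls from 208 to 128, or from about 188 to 116 at the planned retention.

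**The case against.** The best reply is that this is shorthand. SAP section 2 says that the SAP is to be read together with the protocol, the protocol keeps Roll In separate, and SAP 8.2 lists the Roll In Cohort as its own population. SAP 8.5.1 also speaks loosely of randomized Subjects when it describes output for the ITT primary analysis. The sponsor may well have meant completers within ITT. That is plausible as to intent, but a loose phrase in a reporting paragraph does not override an explicit population definition, and the neighbouring definitions show that the SAP states the limit where it wants it.

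Other parts of the reply stand and bound the point. A reader might infer more than the documents support in these ways:

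- *That the trial's conclusion is at risk.* It is not. Success rests on the primary endpoint, whose primary population is ITT. Per-protocol, tipping-point and last-observation-carried-forward analyses are also planned, so Completers is not the only check.
- *That a Completer result would be uninterpretable.* Roll In Subjects are themselves randomized to the two arms, so a randomized comparison remains. The term for their randomization is not defined, and no bias from it is shown.
- *That 38% is the expected share.* Eighty is a ceiling. Protocol 4.4.2 allows up to two Subjects per physician and says that some physicians will have no Roll In phase.
- *That the result would be inflated or diluted by a known amount.* The documents give no Roll In effect. With 58 ITT and 36 Roll In Subjects per arm and a 25-point ITT difference, the pooled difference is (58 × 25 + 36 × d)/94. It runs from 15.4 points (d = 0) to 25.0 points (d = 25), so the answer is whatever one assumes. Nor does the plan claim any power for this supporting analysis.
- *That SAP 7.2 has the same error.* Its complete-data population for the secondary endpoints is not described as all randomized Subjects, and the sentence before it sets ITT as randomized Subjects outside Roll In. No defect is demonstrated there.

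**Conclusion.** The point holds as an error in one definition. As written, SAP 8.2 admits Roll In Subjects to the Completer analyses of the primary and secondary endpoints, against the separate-cohort rule in Protocol Table 1, and nothing else in the documents removes them. The effect is confined to those supporting analyses, where a missing-data effect and a change of population could not be told apart.

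The size depends on how many Roll In Subjects there are, which the documents only cap. At an ITT size of 128 the share is about 14% with 20, 24% with 40 and 38% with the full 80. With 80 it is about a quarter if the interim doubles the ITT size. These shares assume equal completion in the ITT and Roll In groups; the values 20 and 40 are illustrations.

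**What to change.** In SAP 8.2, start the Completer definition from Subjects in the ITT Cohort instead of from all randomized Subjects, and leave the rest of the sentence as it is. State that efficacy in the Surgical Roll In Cohort is reported separately.

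If pooling was in fact intended, the SAP should say so, reconcile it with Protocol Table 1, and add an ITT versus Roll In poolability step for efficacy.

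As an optional clarification, SAP 7.2 could state that its complete-data population lies within ITT.

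The cost is a few words in the SAP and one population flag in the programming, settled before unblinding. It needs no new data and no change to the design, the sample size or the primary analysis.

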Exercise therapy is frequently prescribed for NSLBP, but the effectiveness of exercise therapy for *acute* back pain is negligible.¹⁸ Systematic reviews of the literature^{19,20} concerning therapies for *chronic* low back pain show that exercise is generally ineffective, other than certain types of exercise therapy which can be effective in a small subset of patients.

Many non-invasive conservative therapies have been tried with modest or no success, and several reviews are available.²¹ Therapies include lumbar extensor strengthening exercises,²² watchful waiting (i.e., no therapy),²³ traction therapy,²⁴ the McKenzie Method of exercise therapy,²⁵ various types of energy application including ultrasound, TENS,²⁶ osteopathic therapy,²⁷ and thermotherapy,²⁸ and lumbar stabilization exercises.²⁹

Following failure of conservative therapy for CLBP, “usual care” or “conventional medical management” for CLBP usually consists of coping mechanisms for pain, and pain medications (often opioids), which are often increased during the episodic flare-ups of pain.

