6.8. Visit 8: 120 -0/+20 Days Post Randomization

This Primary Endpoint Assessment Visit must be performed no sooner than 120 days post randomization to ensure all Subjects have at least 120 days of treatment or control. At this visit Subjects in the Control group may now be programmed to appropriate stimulation levels and will be considered part of the Crossover group.

Data to be collected:

- Pain Journal
 - VAS for daily average low back pain
- 7 day recall of Average Low Back Pain VAS as reported by the Subject
- Low Back Pain descriptive characteristics
- Work status evaluation
- Oswestry Disability Index
- EQ-5D
- Pain medications prescribed and taken
- Percent Pain Relief
- Subject Global Impression of Change (SGIC)
- Treatment Satisfaction Questionnaire (TSQ)
- Clinical Global Impression – Global Improvement (CGI-I)
- Adverse events
- Blinding Assessment

Activities to be performed after endpoint data collection:

- Collect Subject's Journal
- Inspection of surgical site (Physical Exam and Surgical Site Exam)
- Device activities:
 - Electrode impedance and threshold measurements
 - Readout from IPG of stimulation delivery times and duration (compliance assessment), battery state, and stored impedance measurements
 - Adjustment of stimulation configuration and amplitude as appropriate
- For Subjects in the Control group, assessment of thresholds and programming of the ReActiv8 IPG to a Subject appropriate level that result in strong smooth contractions of the multifidus. These Subjects now form the Crossover Group.

Note: At the Primary Endpoint Assessment Visit, all Subjects are advised that they can vary their medications for back pain as needed or desired.

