6.1. Sample Size Estimate

The sample size for the study is determined under the following assumptions for the primary efficacy endpoint:

- Minimum power of 80%
- Type I error of 5%
- Assumed primary efficacy success in Treatment group: 50%
- Assumed primary efficacy success in Control group: 25%

Under the above assumptions, a minimum of 116 evaluable Subjects is required in order to demonstrate superiority of the ReActiv8 treatment. The total sample size is increased by 10% to 128 to allow for attrition. The total sample size may be increased, but not decreased, at the time of the planned interim analysis to adjust for updates to the planning assumptions.

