6.2. Level of Power and Significance

All tests of significance will be performed at the two-sided 0.05 significance level. The hypotheses associated with the first five secondary efficacy objectives will be tested using the Hochberg multiple comparison adjustment in the event the primary efficacy objective is met.

7. Data Structure and Handling

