8.9. Supporting Analyses

The supporting efficacy analyses will include:

- Once data are complete, all primary and secondary outcome measures will be assessed at 12 months and compared to baseline within the Treatment group. The analysis will also explore correlation of outcomes to amount of stimulation delivered.

a Cui, L., Hung, H. M., & Wang, S. J. (1999). Modification of sample size in group sequential clinical trials. *Biometrics*, 55, 853–857. doi:10.1111/j.0006-341X.1999.00853.x

Note: For all supporting analyses, amount of stimulation delivered will be defined as the number of minutes stimulation was delivered divided by the number of minutes that stimulation could have been delivered.

- In the Crossover Group, outcome measures will be assessed at the Outcome Post Crossover Visit for all Subjects who met the inclusion criteria for low back pain at the Primary Endpoint Assessment Visit (i.e.: prior to Crossover) (Prior week average Low Back Pain, VAS of ≥ 6.0 cm and ≤ 9.0 cm (on a 10cm scale)) and inclusion criterion for ODI (Oswestry Disability Index score $\geq 21\%$ and $\leq 60\%$). The analysis will also explore correlation of outcomes to amount of stimulation delivered.
- Comparison of daily average VAS averaged over the prior 7 days of Journal entry with the single point VAS of recollection of prior 7 days of average pain.
- Comparison of EQ-5D VAS between Treatment and Control groups at each visit at which EQ-5D is recorded through 12 months.
- For the both the Treatment and Control groups, a cumulative proportion of responder analysis, so that the entire distribution of treatment response is depicted in a graph of the proportion of responders for all percentages of low back pain VAS reduction from 0% to 100%. In this manner, the number of Subjects with $\geq 50\%$ low back pain VAS improvement can be determined, for example. The analysis will also be performed for the responder analysis of ODI.
- Subject Global Impression of Change at 12 months: The analysis will explore correlation of outcomes to amount of stimulation delivered.
- Treatment satisfaction questionnaire at 12 months: The analysis will explore correlation of outcomes to amount of stimulation delivered.
- Clinical Global Impression – Global Improvement (clinician assessment) at 12 months: The analysis will also explore correlation of outcomes to amount of stimulation delivered.

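### The filtered crossover analysis selects Control Subjects on their Visit 8 scores without stating the reference reading for change and without a benchmark, so regression to the mean could pass as a response to stimulation

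*SAP*

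**What the plan says.** - **Filter.** SAP 8.2 forms the Crossover Cohort from "All Subjects in the Crossover Group who met the inclusion criterion 2 for low back pain", with VAS 6.0-9.0 cm, and who also meet the ODI entry range of 21-60%, at the time of crossover.
- **Two analyses under objective 6.** SAP 8.6.6 evaluates changes in all primary and secondary metrics after the Outcome Post Crossover Visit. It covers all Crossover Subjects first, then adds a separate analysis of those who met the VAS and ODI criteria at the Primary Endpoint Assessment Visit (Visit 8).
- **Only the filtered set elsewhere.** In SAP 8.9, "outcome measures will be assessed at the Outcome Post Crossover Visit for all Subjects who met the inclusion criteria for low back pain" (and for ODI). Protocol 4.7.5 and the Protocol synopsis (Table 1, Supporting Analyses) do the same.
- **Reference reading.** None of these sections says which earlier reading the change is taken from.
- **Conditions at Visit 8.** Protocol 6.8 states that "all Subjects are advised that they can vary their medications for back pain as needed or desired". Protocol 4.9 expects Crossover Subjects to become unblinded.
- **Status.** SAP 4 lists this as the sixth secondary objective and attaches no hypotheses to it.

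**The concern.** The filter rests on single readings taken at one visit. Protocol 2.1 describes a condition with flare-ups, in its remark that pain medications are ones "which are often increased during the episodic flare-ups of pain". Some Controls who score 6-9 cm at Visit 8 will be above their usual level that week and will score lower next time whatever the device does. If the same reading is then the starting point for change, that fall is counted as change after crossover.

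Freed medication and the loss of blinding act over the same interval, and no comparison group is planned to show how much of the change they explain. At stake is how a stated secondary objective is read: whether Controls improve once they receive active stimulation.

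**Working it through.** **1. The plan's own figures.** The documents give no number for the Crossover Cohort. The relevant planning inputs are in SAP 6.1 and 6.2: 50% against 25% response, two-sided 5% error, 80% power. With pooled variance and no continuity correction:

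n per arm = [1.960 x sqrt(2 x 0.375 x 0.625) + 0.842 x sqrt(0.25 + 0.1875)]^2 / 0.25^2 = (1.342 + 0.557)^2 / 0.0625 = 57.7, so 58 per arm and 116 in all.

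This reproduces the stated 116. There are therefore about 58 evaluable Controls, or 64 if all 128 randomized Subjects are counted.

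**2. Formula for the artefact.** Suppose two readings share mean m, SD s and correlation r, with no true change. Selecting on the first reading gives

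expected change = -(1 - r) x (mean of selected - m).

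Example with m = 6, s = 2, r = 0.6 and selection on 6-9 cm. The selected mean is 6 + 2 x (0.3989 - 0.1295) / 0.4332 = 7.24. The change is -0.4 x 1.24 = -0.50 cm.

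At m = 7.5, the midpoint of the window, the selected mean is 7.5 and the change is zero. At m = 8.0 it is +0.07 to +0.27 cm over s = 1.5-2.5 and r = 0.4-0.8.

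**3. Calibration to the plan.** The documents do not give the Control mean at Visit 8, so it was set by simulation to make 25% of Controls show a VAS fall of at least 30% from Visit 1 (SAP 6.1). Assumptions not in the documents: normal VAS, with readings after Visit 1 clipped to 0-10 cm; Visit 1 mean 6.5 cm before the 6-9 cm entry selection; SD 1.5-2.5 cm; correlation 0.4-0.8; the same mean at Visit 7, Visit 8 and after crossover; no stimulation effect. The ODI filter and the medication part of the responder definition were not modelled.

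| SD | r | Visit 8 mean, all | Share passing VAS filter | Visit 8 mean, filtered | Change from Visit 8, filtered | Change from Visit 1, filtered | Change from Visit 1, all |
|---|---|---|---|---|---|---|---|
| 1.5 | 0.4 | 5.99 | 48% | 7.04 | -0.71 | -1.01 | -1.22 |
| 1.5 | 0.6 | 5.86 | 45% | 6.94 | -0.59 | -1.10 | -1.35 |
| 1.5 | 0.8 | 5.66 | 37% | 6.77 | -0.40 | -1.33 | -1.55 |
| 2.0 | 0.4 | 6.36 | 50% | 7.28 | -0.65 | -0.77 | -0.97 |
| 2.0 | 0.6 | 6.21 | 50% | 7.20 | -0.57 | -0.85 | -1.12 |
| 2.0 | 0.8 | 5.94 | 47% | 7.01 | -0.45 | -1.09 | -1.39 |
| 2.5 | 0.4 | 6.64 | 46% | 7.40 | -0.56 | -0.58 | -0.75 |
| 2.5 | 0.6 | 6.48 | 48% | 7.34 | -0.52 | -0.64 | -0.90 |
| 2.5 | 0.8 | 6.18 | 50% | 7.18 | -0.46 | -0.88 | -1.21 |

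**4. Reading the table.**
- With Visit 8 as reference, the filtered set falls by 0.40-0.71 cm with no stimulation effect. All Crossover Subjects change by 0.00 cm.
- With Visit 7, a reading not used for selection, as reference, the filtered set changes by 0.00 cm to within simulation error. This confirms that the fall comes from selecting and measuring on the same reading.
- With Visit 1 as reference, the fall is smaller in the filtered set than in all Controls. It then consists of entry regression and sham-period change, so it does not isolate crossover.

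**5. Precision.** The filtered set is about 22-29 of 58 Controls before the ODI filter. At n = 30, SD 2.0 and r = 0.6, the artefact is 0.57 / 0.29 = 2.0 standard errors. Over the grid it runs from 0.56 / 0.39 = 1.4 to 0.71 / 0.26 = 2.7.

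**The case against.** The strongest reply is that the documents never make Visit 8 the starting point. The remark that the criteria are checked before crossover fixes when Subjects are selected, not what change is measured from. The metrics themselves mostly look back to enrolment: the responder definition and ODI use baseline, Percent Pain Relief is relative to baseline (Protocol 4.6.4), and SGIC asks about status since enrolment (Protocol 4.6.5). **This stands.** The artefact is conditional, and the gap is the unstated reference. It does not remove the concern, because a Visit 1 reference does not answer the crossover question either.

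Second, objective 6 is worded for the whole Crossover group, and SAP 8.6.6 puts all Crossover Subjects first. **This also stands**, but SAP 8.9 and Protocol 4.7.5 name only the filtered set, and no section says which result leads.

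A reader might go further in three ways that are not supported:
- *The bias can only favour the device.* It vanishes near a Control mean of 7.5 cm and reverses above it. The medication effect has no fixed direction either: Protocol 4.7.6 notes that some Subjects reduce medication and others increase it, and an increase counts as non-response if the primary definition is carried over.
- *The share of apparent responders is produced by the filter.* With mean 5.0, SD 2.5 and correlation 0.7, about 20% of the filtered set show a 30% fall from Visit 8 with no effect, but so do about 20% of all Crossover Subjects. The filter shifts the mean change.
- *The upper limits aggravate the problem.* In that same setting, removing the 9 cm limit enlarges the spurious fall from 0.69 to 0.80 cm.

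**Conclusion.** The concern holds in a limited form. The filtered analysis leaves its reference reading undefined and has no benchmark. If change is taken from Visit 8, a mean VAS fall of roughly 0.4-0.7 cm is expected from regression to the mean alone. That size depends on the plan's 25% Control response and on the assumed SD and correlation. It is an expectation, not a certainty, given the small cohort and the dependence on the Control mean at Visit 8.

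It would be wrong to infer that the trial's efficacy conclusion is at risk. Objective 6 has no hypotheses, lies outside the Hochberg procedure and plays no part in trial success (SAP 4, 8.5.1 and 8.6). The matter is worth correcting because the remedy is cheap and the result could otherwise be read as evidence of device benefit.

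**What to change.** Amend SAP 8.6.6 and 8.9, and align Protocol 4.7.5:

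1. State that the crossover change is measured from the pre-crossover reading at Visit 8. For Percent Pain Relief and SGIC, whose questions refer back to baseline or enrolment, show the Visit 8 and post-crossover answers side by side. Name the all-Crossover-Subjects analysis as the lead result for objective 6, and say so in SAP 8.9 as well.
2. If the filtered analysis is kept, report beside it the Visit 7 to Visit 8 change under sham in Control Subjects who meet the same VAS and ODI filter at Visit 7. In the model above, with equal means and correlations across visits, this benchmark has the same expected fall as the artefact. Optionally add Treatment Subjects who meet the filter at Visit 8, over the same later interval, as a descriptive comparison only.
3. Report medication change alongside, and label the filtered result as uncontrolled and open to regression to the mean.

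**Cost.** SAP wording and one or two table rows. VAS, ODI and medication are already collected at Visits 7, 8 and 9-11 in both arms (Protocol Table 2).

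**Limits.** Visit 7 to Visit 8 is nominally 120 - 75 = 45 days, against 60 days from Visit 8 to Visit 9 and 120 days to Visit 10. If the post-crossover interval is longer, the benchmark may understate the artefact. It also does not cover freed medication, because medication is meant to stay constant until Visit 8. Treatment Subjects still at 6-9 cm on active stimulation are a differently selected group, so that row is context and not a correction.
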